Mitoxantrone	MITOXANTRONE SANDOZ 2 mg/ml	L01DB07	00664448	0787-804	2 mg/mL; 5 mL drip to dilute	01/09/2013
Mitoxantrone	MITOXANTRONE SANDOZ 2 mg/ml	L01DB07	00664650	0787-812	2 mg/mL; 5x10 mL drip to dilute	01/09/2013
Mitoxantrone		L01DB07	00106292		2 mg/mL; 10 mL drip to dilute	No longer reimbursed since 01/05/2012
Mitoxantrone		L01DB07	00106191		2 mg/mL; 125 mL drip to dilute	No longer reimbursed since 01/12/2007
Mitoxantrone		L01DB07	00531779		2 mg/mL; 12.5 mL drip to dilute	no information
Mitoxantrone		L01DB07	00531880		2 mg/mL; 10 mL drip to dilute	no information
Fingolimod	GILENYA 0,5 mg	L04AA27	00995864	0753-160	0.5 mg; 28 capsules pack	01/02/2012

Fingolimod	GILENYA 0,25 mg	L04AA27	01541286	7726-433	0.25 mg; 28 capsules pack	01/12/2019
Fingolimod	GILENYA 0,5 mg	L04AA27	01541598	7727-472	0.5mg; 28 capsules pack	01/06/2020
Natalizumab	TYSABRI 300 mg	L04AA23	00651516	0787-317	20 mg/mL; 15 mL drip to dilute	01/12/2007
Cladribine	LEUSTATIN	L01BB04	00214915	0760-520	1 mg; 7x10mL drip to dillute	01/06/1999
Cladribine	LITAK 2 mg/ml	L01BB04	00960300	0755-124	2 mg/mL; 5mL injectable solution	01/10/2011
Cladribine	MAVENCLAD 10 mg	L04AA40	01459885	7722-937	1 mg; 1 cp	01/08/2018
Alemtuzumab	LEMTRADA 12 mg	L04AA34	01201079	7709-090	12 mg; 1.2 mL drip to dilute	01/01/2015
Alemtuzumab		L04AA34	00571892		30 mg/mL; 3x1mL drip to dilute	no information
Rituxumab	MABTHERA 100 mg	L01XC02	00226635	0763-177	10 mg/mL; 2x10mL drip to dilute	01/08/2000
Rituxumab	MABTHERA 500 mg	L01XC02	00226736	0763-169	10mg/mL; 50mL drip to dilute	01/08/2000
Rituxumab	MABTHERA 1400 mg	L01XC02	01197948	7708-944	120mg/mL; 11,7 drip to dilute	01/12/2014
Rituxumab	TRUXIMA 500mg	L01XC02	01429457	7721-004	10 mg/mL; 50mL drip to dilute	01/11/2017
Rituxumab	MABTHERA 1600 mg	L01XC02	01459717	7722-135	120mg/mL; 13,4mL drip to dilute	01/04/2018
Rituxumab	TRUXIMA 100 mg	L01XC02	01459764	7722-002	10mg/mL; 2x10mL drip to dilute	01/03/2018
Rituxumab	RIXATHON 100 mg	L01XC02	01459890	7723-349	10mg/mL; 2x10mL drip to dilute	01/10/2018
Rituxumab	RIXATHON 500 mg	L01XC02	01459891	7723-331	10mg/mL; 50mL drip to dilute	01/10/2018
Rituxumab	TRUXIMA 500mg	L01XC02	01541656	7727-746	10mg/mL; 50mL drip to dilute	01/07/2020
Rituxumab	TRUXIMA 100 mg (Abacus)	L01XC02	01541886	7728-256	10mg/mL; 2x10mL drip to dilute	01/09/2020
Ocrelizumab	OCREVUS 300 mg	L04AA36	01510398	7724-305	30mg/mL; 10mL drip to dilute	01/03/2019

14 APPENDIX 2

Appendix 2.1 LIST OF AUTOIMMUNE CONDITIONS

One of the contraindications on the newly revised SmPC is "other concomitant autoimmune (AI) disease". To measure whether patients have "other AI disease" a framework defining diseases that this term may encompass is needed.

We reviewed the epidemiology of AI disease in both a general population and the MS population to construct a broad list of AI conditions. (1-8)

We aimed to make this list as comprehensive and general as possible, and so have not restricted the list by frequency or seriousness of disease. We added to this list a number of rare/serious AI conditions that are listed as safety concerns in the current Risk Management Plan for LEMTRADA (e.g., acquired haemophilia A, IgA nephropathy, anti-glomerular basement membrane disease/Goodpasture Syndrome and hemophagocytic lymphohistiocytosis), or have been subject to discussion with regulatory bodies.

Connective tissue disorders

- Ankylosing spondylitis (M45.*)
- Dermatomyositis/polymyositis (M33.*)
- Polymyalgia rheumatica (M35.3)
- Rheumatoid arthritis (M05.*)
- Sjogren's Syndrome (M35.0*)
- SLE (M32.8)
- Systemic sclerosis (M34.*)
- Wegener's granulomatosis (Granulomatosis with polyangiitis) (M31.3*)
- Churg-Strauss syndrome (M30.1)
- Cutaneous leukocytoclastic angiitis
- Essential cryoglobulinemic vasculitis (D89.1)
- Henoch-Schönlein purpura (D69.0)
- Microscopic polyangiitis (M31.7)
- Kawasaki disease (M30.3)
- Polyarteritis nodosa (M30.0)
- Giant cell (temporal) arteritis (M31.6)
- Raynaud (I73.*)
- Takayasu arteritis (M31.4)
- Behcet's syndrome (M35.2)
- Relapsing polychondritis (M94.1)
- Reactive arthritis (M02.3*)

Endocrine

- Adrenocortical insufficiency (E27.4)
- Type 1 Diabetes (E10)
- Hashimoto's Disease and Grave's disease (E06.3, E05.00)

A PASS to investigate drug utilisation and safety monitoring patterns Study number Prime DUT0008 and VV-PV-0525776

Gastrointestinal

- Autoimmune hepatitis (K75.4)
- Celiac Disease (K90.0)
- Inflammatory Bowel Disease (Crohn's and UC) (K50.* and K51.*)
- Primary Biliary Cirrhosis (K74.3)

Hair and skin

- Alopecia areata (L63.*)
- Phemphigoid/pemphigus (L10.9)
- Psoriasis (L40.0, L40.1, L40.2, L40.3, L40.4, L40.8)
- Vitiligo (L80.0)

Other

- Guillain Barre Syndrome (G61.0)
- Pernicious anaemia (D51.0)
- Autoimmune hemolytic anaemia (D59.1)
- Idiopathic thrombocytopenic purpura (D69.3)
- Acquired haemophilia A
- IgA nephropathy (N02.8)
- Anti-Glomerular basement membrane disease/Goodpasture Syndrome (M31.0)
- Hemophagocytic lymphohistiocytosis (D76.1)
- Myocarditis
- Acute disseminated encephalomyelitis (G04.00)
- IPEX: immune dysregulation, polyendocrinopathy, enteropathy, X-linked
- Thrombotic Thrombocytopenic Purpura (D69.3)
- Rheumatic fever and rheumatic heart disease (I01.*)
- Myasthenia Gravis/Lambert-Eaton syndrome* (G70.0*/G70.80 and G70.81)
- Sarcoidosis (D86.*)

Notes on the above list:

1) chronic gastritis is excluded because it may be mixed with other non-AI forms of gastritis e.g., *H. Pylori* infections.

2) In a sensitivity analysis, thyroid disease will be examined by using ICD-10 code E06.*

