			on prescriptions are inadequate as patients
			may be controlled).
		5.	Recorded comorbidities: arterial dissection
			of cerebral artery (ICD101/7.71), arterial
			ISSECTION OF VERIEDRAL ARTERY (ICD10
			precerebral arteries (ICD10 I77 75) Not
			measurable in Belgian data.
		6.	Recorded comorbidity: all strokes (ICD10
			I60-I63)
		7.	Recorded comorbidity: Angina (ICD10 I20),
		0	Myocardial infarction (ICD10121-123)
		0.	(ICD10 D65-D69) or use of the following:
			Anti-platelet drugs [glycoprotein IIb/IIIa
			inhibitors (e.g., Abciximab, Eptifibatide,
			Orbofiban, Roxifiban, Tirofiban); ADP
			receptor/P2Y12 inhibitors (e.g., Clopidogrel,
			Prasugrel, Ticlopidine, Cangrelor, Elinogrel,
			Licagrelor); prostaglandin analogues (e.g., Beraprost Iloprost Prostaguelin
			Treprostinil): COX inhibitors
			(e.g., Acetylsalicylic acid, aspirin):
			thromboxane inhibitors (e.g., Dipyridamole
			+ aspirin, Picotamide, Terbogrel,
			Terutroban); phosphodiesterase inhibitors
			(e.g., Cilostazol, Dipyridamole, Triflusal)];
			anticoagulants lyitamin K antagonists

Property of the Sanofi Group - strictly confidential
		 (e.g., Warfarin, Acenocoumarol, Coumatetralyl, Dicoumarol, Ethyl biscoumacetate, Phenprocoumon, Diphenadione); factor Xa inhibitors (Heparin group / glycosaminoglycans / bind antithrombin: e.g., Bemiparin, Certoparin, Dalteparin, Enoxaparin, Nadroparin, Parnaparin, Reviparin, Tinzaparin, Fondaparinux, Danaparoid, Dermatan sulfate, Sulodexide); direct Xa inhibitors (e.g., Apixaban, Betrixaban, Edoxaban, Rivaroxaban); direct thrombin IIa inhibitors (e.g., Hirudin, Bivalirudin, Desirudin, Argatroban, Dabigatran, Efegatran); antithrombin III]; thrombolytic drugs / fibrinolytics [e.g., Alteplase, Reteplase, Tenecteplase, Saruplase, Urokinase, Brinase, Fibrinolysin]. ATC codes for drugs provided in SAP. 9. Recorded AI disease: please see rationale for list in attached Appendix 2 	
2a and 2b Monitoring if	Prior to Infusion	Prior to infusion	
after new label	Baseline ECG, vital signs including HR and BP	Data on ECG, HR and BP will be measured	
	Perform laboratory tests (FBC with differential, serum creatinine, serum transaminases, urinalysis with microscopy, and test of thyroid function).	prior to the index date (index date included), for each course. The test dates closest to course start date will be taken.	

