9.8.4 Other Analyses (Subgroup/Stratified and Sensitivity Analyses)

For all objectives we will carry out the following subgroup/stratified analyses, where cell size permits:

- Stratified by age group and gender.
 - Age groups to be defined during full feasibility analysis.
- Stratified by the year of index date.
 - For objective 2b, analyses will be stratified by calendar year that monitoring is intended to occur (2020, 2021, 2022, 2023 and (Q1) 2024) to understand how the Covid-19 pandemic may have impacted monitoring. The analysis should consider the year of infusion.
- For objectives 1b, 2a, and 2b, analyses will be stratified by new or continuing use.
- For objectives 1b, 2a, and 2b, analyses will be stratified by course number (first, second, third, etc).
- For objective 1b, analyses will be stratified by individual contraindications.
- For objective 2b, analyses will be stratified by time period.
- For objective 2a, a sensitivity analysis will evaluate the proportion of courses with monitoring tests at least 1 day prior to index date (i.e. period excluding index date). This analysis will be done for each monitoring test that is recommended per SmPC both prior to the course initiation and during the course (i.e. HR and BP). The results will provide a more conservative estimate by considering patients with a test only at index date as not adherent for prior testing.
- For objective 2b, sensitivity analysis will be carried out counting from the last available testing date instead of the index date for the window when the subsequent test is expected.

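### The autoimmune code list behind primary objective 1b repeats one code for two diseases, gives single or gapped sub-codes where its neighbours use whole categories, and overlaps with the coagulopathy range

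*Protocol*

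**What the plan says.** Section 9.8.1 of the protocol defines the 1b numerator as courses with none of the contraindications at the index date. Table 2 (section 9.3) lists nine contraindications. Item 8, known coagulopathy, is defined as "ICD10 D65-D69) or use of the following", followed by drug classes. Item 9, other autoimmune disease, refers to Appendix 2.

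Appendix 2.1 states its purpose: "We aimed to make this list as comprehensive and general as possible". Among its entries are:

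- "Idiopathic thrombocytopenic purpura (D69.3" and, further down the same group, "Thrombotic Thrombocytopenic Purpura (D69.3"
- "Henoch-Schönlein purpura (D69.0"
- SLE, with M32.8 only
- "Phemphigoid/pemphigus (L10.9"
- "Psoriasis (L40.0, L40.1, L40.2, L40.3, L40.4, L40.8"

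Other entries carry a wildcard for the whole category, for example M33.*, M34.*, M45.*, L63.* and K50.*.

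Section 9.8.4 adds the breakdown: "For objective 1b, analyses will be stratified by individual contraindications".

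**The concern.** Objective 1b is primary, and its numerator counts courses in which nothing was found. Any autoimmune disease that the search fails to pick up is therefore scored as compliance. In a study meant to verify risk minimisation, that is the reassuring direction.

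The list appears faulty in two ways that could cause this: a code repeated for two separately named diseases, and narrow codes for a few diseases in a list that otherwise takes whole categories. A third feature affects reporting only. The coagulopathy range contains codes that the appendix classes as autoimmune, so the same record qualifies under two contraindications. The TREAT-MS observation plan (Background) names idiopathic thrombocytopenic purpura among the autoimmune diseases to which treated patients are at risk, so its place in the breakdown matters for continuing courses.

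**Working it through.** The plan states no figure for misclassified or doubly counted courses, so there is nothing to reproduce. The check compares the printed codes and then adds simple arithmetic on Table 5.

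**1. Duplicate code.** Appendix 2.1 gives D69.3 to both idiopathic and thrombotic thrombocytopenic purpura. The list treats them as two conditions, so either one code is wrong or one entry is redundant.

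**2. Breadth of codes.** Systemic sclerosis, dermatomyositis/polymyositis, ankylosing spondylitis and alopecia areata are searched as whole categories. SLE is searched at one sub-code. Pemphigoid and pemphigus, two named diseases, share one sub-code. Psoriasis runs from L40.0 to L40.4 and then jumps to L40.8. No reason is given, whereas the omission of chronic gastritis is explained in a note. The same notes plan a sensitivity analysis that widens the thyroid code to E06.*, so the protocol itself treats code breadth as something that can change the result, but only for thyroid disease.

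**3. Overlap.** Three Appendix 2.1 entries as printed fall inside D65-D69: Henoch-Schönlein purpura (D69.0) and the two purpuras coded D69.3. One such code meets items 8 and 9 of Table 2 together.

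Illustration with assumed numbers: 100 courses, 10 of them contraindicated, of which k qualify only through D69.0 or D69.3 and the rest through one contraindication each.

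- Headline 1b = (100 − 10)/100 = 90% for every k, because a course counts once however many rows it meets.
- Sum of the breakdown rows = 10 + k, that is 11, 12 or 13 for k = 1, 2, 3.

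**4. Where the codes are used.** Patients in cohort 1b at the 2023 interim (Table 5): AIM-IMA 87, ReMuS 107, UK 69, TREAT-MS 72, total 335.

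- Belgium (Appendix 1) holds no diagnoses and uses drug proxies with specialist review. TREAT-MS (Appendix 4) uses MedDRA terms. Together (87 + 72)/335 = 159/335 = 47.5% are outside the ICD-10 list.
- ReMuS charts (section 9.5.1) hold ICD-10 codes or plain text: 107/335 = 31.9%. Without Belgium, which gets no new analysis, the share is 107/(335 − 87) = 107/248 = 43%.
- For the UK (section 9.5.4) no coding system is stated. If its charts are matched to ICD-10, the reach becomes (107 + 69)/335 = 176/335 = 52.5%.

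**5. Size of one miss**, with patients standing in for courses and the patient having no other contraindication: 1/107 = 0.93 points in ReMuS, 1/69 = 1.45 in the UK, 1/335 = 0.30 overall.

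**6. Total size.** Overstatement = p × (1 − c) at most, where p is the share of courses with an affected disease and c the share of those caught by the listed codes. The protocol gives neither. Purely assumed ranges of p = 2-8% and c = 40-80% would give 0.02 × 0.2 = 0.4 points to 0.08 × 0.6 = 4.8 points. This shows how the result depends on its inputs and is not an estimate.

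**The case against.** The strongest reply is that the list is led by disease names. Several entries, such as acquired haemophilia A and myocarditis, have no code, so chart reviewers cannot be working from codes alone. Table 2 introduces its codes as non-exhaustive, ReMuS contraindications are extracted manually, and plain text naming lupus or psoriasis would be recognised. Source-specific definitions are left to the local operating protocols. This stands as a limit on the effect: missed cases are possible, not shown. It does not remove the defect, because leaving capture to local discretion sits badly with the aim in section 9.7.2 of identical calculations in every database.

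Stronger readings are tempting but unsupported:

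- A reader might infer that thrombotic thrombocytopenic purpura is never searched. Both purpuras are on the same list for the same contraindication, so a record coded D69.3 is caught either way. A case is lost only if it is coded elsewhere, which the protocol does not say.
- A reader might infer that the D69 overlap biases 1b or moves idiopathic thrombocytopenic purpura out of the autoimmune row. The headline is a union, and the disease still appears in the autoimmune row. Rows may also overlap legitimately when a course has several contraindications. What remains is that here a single diagnosis produces two entries and no rule says how to present it.
- A reader might extend the point to rheumatoid arthritis. That entry (M05.*) is already a whole category, and the protocol offers no internal sign that it is too narrow.

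Exactly which sub-codes are left out for SLE, pemphigoid/pemphigus and psoriasis depends on the ICD-10 classification, which the protocol does not reproduce. The inconsistency with the list's own practice can be seen without it.

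**Conclusion.** The point holds in limited form. The duplicated D69.3, the narrow entries for SLE and pemphigoid/pemphigus, the gapped psoriasis list and the D69 overlap are all in the current text.

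The narrow entries could overstate the 1b proportion, but only where records are matched by ICD-10 code: part of ReMuS (107 of 335 interim patients) and possibly the UK. The size cannot be derived from the protocol. The only firm scale is about 0.9 points per missed patient in ReMuS. This rests on three assumptions: other sub-codes for these diseases are in use, plain text does not recover the case, and the patient has no other contraindication. The overlap affects only the section 9.8.4 breakdown and leaves the headline unchanged.

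Correction is worthwhile because the objective is primary, any error from missed cases runs in the favourable direction, and the remedy is cheap.

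**What to change.** - Verify D69.3 for both purpuras and correct or merge the entries.
- Use whole categories for SLE, psoriasis, and pemphigus and pemphigoid, as the list does for their neighbours, or give a reason for the chosen sub-codes.
- State whether D69.0 and D69.3 are reported under coagulopathy or autoimmune disease in the section 9.8.4 breakdown. Alternatively, show them under both with a note giving the number of courses that overlap.

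The cost is an edit to the code list and a rerun in ReMuS, and in the UK if its charts are matched to ICD-10. The 1b figure may become slightly less favourable.

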1. BACKGROUND

Manifestation

Multiple sclerosis (MS) is an immune-mediated chronic inflammatory disease of the central nervous system, characterised histopathologically by different degrees of demyelination and axonal damage.^{1,2} MS is the most common neurological disease causing permanent disability and early retirement in the young adults.¹

The clinical course of the disease is variable and cannot be predicted for the given individual. In about 85% of the persons affected the disease is manifested as relapsing-remitting MS (RMS or RRMS). In these cases, clearly distinguishable exacerbations occur at irregular intervals, separated by phases free of symptoms or with few symptoms.² Untreated RRMS advances to the secondary progressive form (SPMS) after about 10 years in at least 50% of patients.

Treatment options

At this time, MS is incurable. The approved medications for long-term disease modifying therapy (DMT) make it possible to decrease attacks, retard disease progression and thus achieve reduced rates of disability in some patients. For disease-modifying treatment of RRMS, the 2012 DGN/KKNMS guidelines recommend beta-interferon Ia or Ib (IFN, for intramuscular or subcutaneous injection) or glatiramer acetate (GA, subcutaneous injection), and only with certain limitations, azathioprine (oral therapy: limited approval, poor data situation, risk of cancer in long-term therapy) as well as immunoglobulins (intravenous therapy).³ Since October 2013 teriflunomide (Aubagio[®]) has been available as an additional alternative.

LEMTRADA® (alemtuzumab) as a new treatment option for active RRMS

 LEMTRADA[®] (alemtuzumab) (ATC-Code: L04AA34) is a selective immunosuppressant and has been approved by the European Medicines Agency (EMA) since September 2013 in Germany for treating adult patients with relapsing-remitting MS defined according to clinical findings or imaging.

LEMTRADA[®] (alemtuzumab) is a monoclonal antibody that is administered intravenously. It binds to CD52, an antigen expressed in large amounts on T- and B-

Observation plan

lymphocytes and also occurs to a smaller degree also on the cell surface of natural killer cells, monocytes and macrophages. The mechanism by which LEMTRADA[®] exerts its therapeutic effect on MS has not yet been fully explained. However, research points in the direction of immunomodulatory effects due to the depletion and repopulation of lymphocytes, including^{8,9,10}

- Changes in the number, fractions and properties of some lymphocyte subgroups after treatment
- Elevated fractions of regulatory T-cell subgroups
- Increased fractions of memory T and B lymphocytes
- Transient effects on components of innate immunity (e.g., neutrophils, macrophages, natural killer cells)

The selective depletion of the circulating B and T cells by LEMTRADA[®] and the subsequent repopulation might be responsible for the therapeutic effect.

The safety and effectiveness of LEMTRADA[®] (alemtuzumab) were investigated in 3 randomised, observer-blinded clinical studies with active comparator in patients with RRMS (Study 1: Phase II - CAMMS223 ⁴;. Study 2: Phase III - CARE-MS I ⁵; Study 3: Phase III - CARE-MS II ⁶).

In line with the effect on the exacerbation rate, supporting analyses from Study 1 (CAMMS323) show that patients treated with LEMTRADA[®] 12 mg/day experienced significantly fewer severe exacerbations compared with IFNB-1a (61% decrease, p = 0.0056) and significantly fewer exacerbations when treated with steroids (58% decrease, p < 0.0001).

Supporting analyses from Study 2 (CAMMS32400507) showed that patients treated with LEMTRADA[®] 12 mg/day compared with IFNB-1a had significantly fewer severe exacerbations (48% decrease, p = 0.0121) and significantly fewer exacerbations when treated with steroids (56% decrease, p < 0.0001) or requiring hospitalisations (55% decrease, p < 0.0045).

A prolonged reduction in disability (Sustained Reduction in Disability, SRD) was shown in Study 3: After 3 years, LEMTRADA[®] reduced the risk of 6-month accumulation of disability (Sustained Accumulation of Disability, SAD) by 76% (Hazard Ratio: 0.24 [95% CI: 0.110; 0.545], p < 0.0006) and reduced the annual exacerbation rate by 67% (incidence density rate: 0.33 [95% CI: 0.196; 0.552], p < 0.0001) compared with subcutaneously administered IFNB-1a. Over 2 years of follow-up LEMTRADA[®]

Observation plan

12 mg/day compared with subcutaneously administered IFNB-1a led to significantly lower EDSS values (improved compared with baseline) (p < 0.0001). After 5 years, LEMTRADA[®] reduces the risk of an SAD by 69% (Hazard Ratio: 0.31 [95% CI: 0.161; 0.598], p = 0.0005) and reduces the annual exacerbation rate by 66% (incidence density rate: 0.34 [95% CI: 0.202; 0.569], p < 0.0001) compared with subcutaneously administered IFNB-1a.

Thus the efficacy of LEMTRADA[®] (alemtuzumab) in RRMS patients with an EDSS of less than 3 (CARE-MS I) and less than 5 (CARE-MS II) was demonstrated impressively. The most important clinical results of the two Phase III studies are represented in the table below.⁷

Observation plan

	Stuc	ly 1	Study 2					
Study title	CAMM	1S323	CAMMS32400507					
-	(CARE	-MS I)	(CARE-	MS II)				
Clinical endpoints	LEMTRADA	IFNB-1a	LEMTRADA	IFNB-1a				
-	12 mg	SC	12 mg	SC				
	(N=376)	(N=187)	(N=426)	(N=202)				
Relapse rate ¹	0,18	0.39	0,26	0,52				
Annual relapse rate (ARR)	(0.13; 0.23)	(0.29; 0.53)	(0.21; 0.33)	(0.41; 0.66)				
(95% CI)								
Incidence density ratio	0.45 (0.3	32; 0.63)	0.51 (0.39; 0.65)					
(95% CI)	54	.9	49.	4				
Risk reduction	(p<0.0	0001)	(p<0.0	001)				
Disabilities ²	8.0%	11.1%	12.7%	21.1%				
(Sustained accumulation of	(5.7; 11.2)	(7.3; 16.7)	(9.9; 16.3)	(15.9; 27.7)				
disability [SAD] over 6 months ¹)								
Confirmed patients with								
SAD over 6 months (95% CI)								
Risk ratio	0.70 (0.4	0; 1.23)	0.58 (0.38; 0.87)					
(hazard ratio; 95% CI)	(p=0	.22)	(p=0.0	084)				
Relapse-free patients after	77.6%	58.7%	65.4%	46.7%				
2 years	(72.9; 81.6)	(51.1; 65.5)	(60.6; 69.7)	(39.5; 53.5)				
(95% CI)	(p<0.0001)		(p<0.0001)					
Change in EDSS from baseline	-0,14 0,14		0,17	0,24				
after 2 years;	(-0.25; -0.02)	(-0.29; 0.01)	(-0.29; -0.05)	(0.07; 0.41)				
Estimate (95% CI)	(p = 0.42)		(p<0.0001)					
MRT endpoints (0-2 years)		I	1	1				
Mean percent change in the	-9,3	-6,5	-1,3	-1,2				
volume of the T2 lesion	(-19.6; -0.2)	(-20.7; 2.5)	(p = 0.14)					
	(p = 0.31)							
Patients with new or enlarging	48.5 %	57.6%	46.2%	67.9%				
T2 lesions over 2 years	(p = 0.035)		(p<0.0001)					
Patients with gadolinium-	15.4%	27.0%	18.5%	34.2%				
enhancing lesions over 2 years	(p = 0.001)		(p<0.0001)					
Patients with new T1	24.0%	31.4%	19.9%	38.0%				
hypointense lesions over	(p = 0.055)		(p<0.0001)					
2 years								
Mean percent change in brain	-0.867	-1.488	-0.615	-0.810				
atrophy	(p<0.0001)		(p = 0.012)					

¹ Co-primary endpoints: ARR and SAD. The study was considered as being successful if at least one of the two co-primary endpoints was reached.

² The time to occurrence of SAD was defined as an increase by at least 1 point on the Kurtzke expanded disability status scale (EDSS) beginning with a baseline EDSS value of ≥ 1.0 (increase by 1.5 points in patients with a baseline EDSS value of 0), lasting for over 6 months.

In summary, LEMTRADA[®] (alemtuzumab) improved the clinical course of MS by decreasing the disease activity (among other things, reduced number of

Observation plan

exacerbations), slowed the progression of the disability and reduced the number of cerebral lesions in the magnetic resonance tomography (MRT) scans.

A total of 1,188 patients with RRMS treated with LEMTRADA[®] (either 12 mg or 24 mg) formed the safety population in a pooled analysis of controlled clinical trials that provided 2,363 patient-years of safety observation and a median follow-up time of 24 months.

The most significant adverse effects are autoimmunity, infusion-associated reactions (IAR) and infections.

The most common adverse effects under LEMTRADA[®] (in $\ge 20\%$ of patients) are rash, headache, fever and respiratory infections.⁷

Up to one third of all patients are at risk of developing antibody-mediated autoimmune diseases, especially in the first four years after the final infusion. These include:

- Thyroid disorders
- Idiopathic thrombocytopenic purpura (ITP, immune thrombocytopenia)
- Nephropathies, including Goodpasture syndrome (anti-GBM disease: Autoantibodies against the basal membrane of the blood vessels, especially in the area of the renal glomeruli and the pulmonary alveoli)

These diseases can usually be treated effectively. Nevertheless these events can be serious and lead to morbidity and/or mortality; they may also not be manifested until many years after treatment.

Currently there are no known surrogate markers that can predict a higher individual risk for developing these secondary autoimmune diseases.

Early diagnosis offers the best chance of successful treatment. To monitor the patients for early signs of autoimmune disease, according to the Summary of Product Characteristics, the blood count and renal function as well as thyroid function should be checked before the beginning of treatment with LEMTRADA[®] or at regular intervals during the treatment, and for 48 months after the last phase of treatment with LEMTRADA[®], blood count and renal function should be checked monthly and additionally thyroid function should be checked every three months. In addition, the treating physician should pay close attention to signs and symptoms.

Furthermore, pregnancy should be prevented for up to four months following a treatment phase.

Observation plan

Overview of laboratory t	tests during	LEMTRADA [®]	therapy
--------------------------	--------------	-----------------------	---------

Disease	Measure	Time	
Idiopathic thrombocytopenic purpura (ITP)	Complete blood count with differential count	Before the beginning of treatment with LEMTRADA [®]	Monthly up to 48 months after the last infusion
Nephropathies, including Goodpasture syndrome	Serum creatinine	Before the beginning of treatment with LEMTRADA [®]	Monthly up to 48 months after the last infusion
Nephropathies, including Goodpasture syndrome	Urinalysis with microscopic sediment analysis	Before the beginning of treatment with LEMTRADA [®]	Monthly up to 48 months after the last infusion
Thyroid disorders	Thyroid function tests (e.g., TSH)	Before the beginning of treatment with LEMTRADA [®]	Every 3 months up to 48 months after the last infusion

LEMTRADA[®] is administered as a solution for infusion in two phases on 5 successive days (at the beginning of treatment) and 3 successive days (from the end of the second treatment phase). There is a one-year treatment-free interval between the first and second treatment phases. According to the Summary of Product Characteristics (as of July 2018), up to 2 additional treatment phases can be considered as needed.

According to the Summary of Product Characteristics, the patients should be pretreated on each of the first 3 days after each of the treatment phases immediately before the administration of LEMTRADA[®]. In addition, pre-treatment with antihistamines and/or antipyretics before administration of LEMTRADA[®] should be considered. Oral prophylaxis against herpes infections should be performed in all patients.

Since LEMTRADA[®] (alemtuzumab) is an immunomodulating medication, it is recommended that the patient should have met the regional immunisation requirements at least 6 weeks before initiation of treatment with LEMTRADA[®]. Patients who have no history of chickenpox and have not been immunised against the varicella zoster virus (VZV) should be tested for antibodies to VZV before the beginning of the

Observation plan

treatment phase with LEMTRADA[®]. VZV vaccination of antibody-negative patients 6 weeks before the beginning of treatment with LEMTRADA[®] should be considered.

First blood and urine tests prior to treatment		→ and in the 4	years after the	last infusion					
(1. Treatment phase	2. Treatment phase							
	5-daily treatment	3-daily treatment							
	Year 1	Year 2	Year 3	Year 4	Year 5				
NOTE In most patients, 2 treatment phases have an effect for 2 years or longer									
	TREATMENT FOLLOW-UP	EXAMINATIONS							

Risk Management Plan

As part of the Risk Management Plan (RMP), a guideline has been developed for prescribing physicians and other specialist medical staff involved in the care of patients treated with LEMTRADA®. This is intended to provide more specific information about the possible serious risks associated with treatment with LEMTRADA®. In addition, the regular monitoring needed to provide for clinical vigilance should also be clarified. Sanofi has made guidelines available for patients as well as for physicians and other specialist medical staff.

The multidimensional Multiple Sclerosis Documentation System (MSDS^{3D}) of the MSDS Project Group in Dresden is used for documenting the patient data in accordance with the Risk Management Plan and SPC.¹¹ This system is a software package that permits standardised management and documentation of the patient and can serve as a data input system for various databases.

Database, data processing and data sharing for the MSDS^{3D}-TREAT module

Collection in the TREAT-MS study can take place as local documentation with the MSDS^{3D}-TREAT module or by means of an internet-based WEB-TREAT eCRF system.

• The patient data to be documented with the internet-based WEB-TREAT eCRF system are obtained in pseudonymised form within the framework of the

Observation plan

TREAT-MS study. The patient data are provided with a code (pseudonym). This is a non-descriptive identifier for a patient. Only the physicians and persons authorised by the project manager who are involved in conducting the research project have access to this code.

 The patient data collected with the MSDS^{3D}-TREAT module system will initially be stored locally within the framework of the TREAT-MS study and sent in pseudonymised form for evaluation and further processing to the MSDS^{3D} registry server of the MedicalSyn GmbH. The data collected are stored throughout the project period both locally in the project centres by means of the MSDS^{3D}-TREAT module and on the MSDS^{3D} registry server of the MedicaSyn GmbH within the framework of the TREAT-MS study.

As soon as the patient's consent for storing the data collected in the MSDS^{3D}-TREAT module (separate patient information and consent form) is available, the data obtained within the framework of the TREAT-MS study are incorporated into the MSDS^{3D}-TREAT database. The MSDS^{3D}-TREAT database is made available by MedicalSyn GmbH Stuttgart on behalf of Carl Gustav Carus Management GmbH Dresden, implementing body Dresden University Hospital, Clinic for Neurology, Centre for Clinical Neurosciences.

The data in the TREAT-MS study server are provided with a code (pseudonym). This is a non-descriptive identifier for a patient. Only the physicians and persons authorised by the project manager who are involved in conducting the research project have access to this code.

Additional patient-related information (age, sex, medical history, diagnosis, history of current illness, clinical course and treatment data) are likewise provided with this code and stored and managed on the MSDS^{3D}-TREAT study server. In this way, protection of the samples from loss, destruction, alteration and access by unauthorised persons is guaranteed.

Confidentiality of data

The collection, transmission, storage and evaluation of patients' personal information within the research project will take place according to the applicable German data

Observation plan

protection provisions. The prerequisite for this is the voluntary consent of the study participants within the framework of consenting to participate in the TREAT-MS study.

The medical data collected from study participants must be treated in the strictest confidence and may not be divulged to third parties.

Confidentiality is guaranteed by the use of codes. All patients are encoded with an alphanumeric code (pseudonymised).

The data to be evaluated are provided with this code only and stored in a data sheet on an MSDS^{3D}-TREAT study server with access limited to the MSDS^{3D} Developer Group of the Department for Neurology and MS Research at the University of Dresden Hospital. Only authorised persons have access to the original data.

Data collected within the framework of this project can be viewed for checking or inspection by the independent ethics committee.

Observation plan

